3 STUDY SIZE

All the patients treated with this drug will be included in the all patient surveillance to be conducted for a specific period of time.

- Target number of cases: 600 cases
- Target number of cases observed: 300 cases treated for 12 weeks or longer (300 cases with Booklet 03 case report form)
(Cases who discontinued the drug before 12 weeks will also be included.)

[Rationale]

The incidence of all the adverse events included in the major investigation items of this study was 1.0% or higher in the drug group of the foreign phase 3 clinical study (304-WW Study). Assuming that the true incidence of an adverse event (particularly an adverse event included in the major investigation items) is 1.0%, 300 cases are required to observe at least 1 case with the event at a probability of at least 95%. The incidence of interstitial lung disease was 17.1% (14/82) in the multinational (Asian) phase 2 clinical study (2217-AP Study).

Assuming that the true incidence of interstitial lung disease is 17.1%, at least 40 cases with the disease can be observed at a probability of at least 95%.

Further, clinical study results showed that interstitial lung disease occurred on Week 4 after the start of the drug or later, and that, in rare cases, some adverse events had an increased incidence or delayed onset as the administration period was prolonged. Considering these results, it was decided to set a target that this study would include 300 cases treated with this drug for 12 weeks or longer.

Clinical study results showed that this drug could be continued for 12 weeks or longer in about 60% of the whole treated cases, with a discontinuance/drop-out rate at 12 weeks of about 40%. Considering that this study will be conducted under actual use condition, it is assumed that the discontinuance/drop-out rate at 12 weeks in this study will be increased by 10% to 50%. That is, it is assumed that this drug will be continued for 12 weeks or longer (the Booklet 03 case report form will be collected) in 50% of the cases included in this study.

Therefore, this surveillance was planned to register 600 cases to collect 300 cases treated with this drug for 12 weeks or longer. In addition, because cases which discontinue the drug before 12 weeks will be included in the study, the case report form will be collected from them to evaluate safety and effectiveness.

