5.4 Observation period

The observation period for this study will be set until Week 24 after the start of administration (cases treated with the drug for more than 25 weeks will be included in the separately planned Special Investigation on long-term use and observed for up to 96 weeks after the start of administration)

[figure not shown]
Clinical evaluation of tumor: Weeks 8, 16, and 24. For discontinued cases, if the clinical evaluation of tumor is not performed within 4 weeks prior to discontinuation, clinical evaluation of tumor will be performed at the time of discontinuation.

Adverse events: Until Week 24 after the start of administration. If the drug is discontinued before Week 24, observe until Day 28 after the discontinuation of administration.

This study will be conducted using a case report form divided into separate booklets. The results during the following observation periods will be recorded in the different booklets of the case report form.

| Booklet | Observation period |
|------------|---|
| Booklet 01 | Start of administration to Week 4 (Day 28) |
| Booklet 02 | Week 5 (Day 29) to Week 12 (Day 84) after start of administration |
| Booklet 03 | Week 13 (Day 85) to Week 24 (Day 168) after start of administration |

(Start of administration)
(Day 1)

Observation period and evaluation time points for each booklet of case report form

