### **2.1.2. Long-term Use Surveillance**

This study is a non-interventional study in a cohort of patients who were registered in the all patient surveillance and received this drug for unresectable or metastatic renal cell carcinoma for more than 24 weeks.

*Among the patients registered and treated in the all patient surveillance, those to be continuously treated with this drug for more than 24 weeks will be included in this study. That is, the target number of cases to be registered in the all patient surveillance is 600 (rationale stated in the protocol of the all patient surveillance) and those to be continuously treated for more than 24 weeks will be registered again in this study. Therefore, no definite target number of cases is set for this study. However, the expected number of cases to be registered in this study is shown below and considered as the target number of cases to be registered.*

*Expected number of cases: about 120 cases*

*[Rationale]*

*The expected number of cases to be registered in this study is described. In the clinical trials, (304-WW and 2217-AP Studies), about 35% of the subjects could be continuously treated for 24 weeks or longer, with a discontinuance/drop-out rate at 24 weeks being about 65%. Considering that the all patient surveillance will be conducted under actual use condition, and that it is necessary to re-register from all patient surveillance to this study, it is assumed that the discontinuance/drop-out rate at 24 weeks in the all patient surveillance will be further increased by 15% to 80%. That is, it is assumed that 20% of the cases included in the all patient surveillance will be registered in this study after the completion of the all patient surveillance. It is therefore expected that about 120 cases will be registered in this study when 600 cases will be registered in the all patient surveillance. However, the actual number of cases registered may be different from the expected number because it depends on the conditions and results of the all patient surveillance.*

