# **6. ENDPOINTS AND COVARIATES**

## **6.1. Safety Endpoints**

1. *Onset state of adverse events/adverse reactions (particularly the major investigation items).*
2. *Onset state of adverse reactions and potential influencing factors (particularly the major investigation items).*
3. *Safety in patients with special background (pediatric patients, elderly patients, pregnant women, patients with renal or hepatic dysfunction).*
4. *Safety in patients with hepatic dysfunction (including the comparative examination with results from the foreign phase 1 clinical study).*
5. *Onset state of interstitial lung disease (including asymptomatic cases with imaging findings of the disease).*

6. *Potential risk factors of interstitial lung disease.*
7. *Characteristics of interstitial lung disease (imaging findings, onset timing, duration, and breakdown by severity).*
8. *List of clinical course of interstitial lung disease (contents of treatment, response to treatment, and outcome) and clinical course after the drug is restarted (presence/absence of recurrence/exacerbation, etc.).*
9. *Onset state of various related events suspected of causing interstitial lung disease (pneumonitis/lung infiltration and pulmonary fibrosis, etc.).*
10. Duration of treatment (Defined as the period from the date of initiation of treatment with this drug to the date of completion of treatment with this drug in this study. Patients for whom the completion of treatment is not reported in this study will be censored at the date of last dose.).

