### **8.2. Statistical Analyses**

Unless otherwise specified, data from the all patient surveillance and data from the long-term use surveillance will be tabulated and analyzed together.

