The number of patients with CTCAE Grade  $\geq 3$  adverse reactions and the incidence of CTCAE Grade  $\geq 3$  adverse reactions will be tabulated by SOC and PT by category shown below. •Further tabulation of serious adverse reactions” will be followed for categories.

- Seriousness;
- Known/unknown;
- Outcome;
- Timing of initial onset;
- Intervention;
- Administration of this drug;
- Duration of treatment;
- Total dose.

- **Further tabulation of adverse events**

The number of patients with adverse events and the incidence of adverse events will be tabulated by SOC and PT by category shown below. “• Further tabulation of serious adverse reactions” will be followed for categories.

- CTCAE Grade.

- **Further tabulation of unknown adverse reactions**

The number of patients with unknown adverse reactions and the incidence of unknown adverse reactions will be tabulated by SOC and PT by category shown below. “•Further tabulation of serious adverse reactions” will be followed for categories.

- Outcome.

- **Cumulative incidence of adverse reactions**

The cumulative incidence of adverse reactions will be graphically presented with the time to onset on the horizontal axis.

The cumulative incidence will be graphically presented in the same manner for interstitial lung disease, diabetes mellitus/hyperglycemia, hypercholesterolemia/hyperlipidemia, infection, mucositis-related adverse events, and skin disorder among major investigation items.

- **Cumulative incidence of CTCAE Grade  $\geq 3$  adverse reactions**

The cumulative incidence of CTCAE Grade  $\geq 3$  adverse reactions will be graphically presented with the time to onset on the horizontal axis.

The cumulative incidence will be graphically presented in the same manner for interstitial lung disease, diabetes mellitus/hyperglycemia, hypercholesterolemia/hyperlipidemia, infection, mucositis-related adverse events, and skin disorder among major investigation items.

- **Incidence of adverse reactions by patient demographic**

The number of patients with adverse reactions and the incidence of adverse reactions will be tabulated by item listed in “[Section 10.1.1. Patient demographics to be used to evaluate safety and efficacy.](#)”

Fisher’s exact test will be performed for nominal scale data and Cochran-Armitage test (exact method) for ordered scale data.

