Tabulation will be performed in the same manner for interstitial lung disease, diabetes mellitus/hyperglycemia, hypercholesterolemia/hyperlipidemia, infection, mucositis-related adverse events, and skin disorder among major investigation items.

For items using reference laboratory test values, results using corporate reference values will be tabulated in addition to results using institutional reference values.

- **Incidence of CTCAE Grade  $\geq 3$  adverse reactions by patient demographic**

The number of patients with CTCAE Grade  $\geq 3$  adverse reactions and the incidence of CTCAE Grade  $\geq 3$  adverse reactions will be tabulated by item listed in “[Section 10.1.1. Patient demographics to be used to evaluate safety and efficacy.](#)”

Tabulation will be performed in the same manner for interstitial lung disease, diabetes mellitus/hyperglycemia, hypercholesterolemia/hyperlipidemia, infection, mucositis-related adverse events, and skin disorder among major investigation items.

For items using reference values, results using corporate reference values will be tabulated in addition to results using institutional reference values.

- **Incidence of adverse reactions by medical history, prior treatment history, and concomitant therapy**

The number of patients with adverse reactions and the incidence of adverse reactions will be tabulated by category shown below.

The number of patients and incidence will be tabulated in the same manner for interstitial lung disease among major investigation items.

- Past medical history;
- Complications;
- Prior medications.

- **Incidence of CTCAE Grade  $\geq 3$  adverse reactions by medical history, prior treatment history, and concomitant therapy**

The number of patients with CTCAE Grade  $\geq 3$  adverse reactions and the incidence of CTCAE Grade  $\geq 3$  adverse reactions will be tabulated by category shown below.

- Past medical history;
- Complications;

- Concomitant medications;
- Non-drug therapies;
- Prior medications.
- **Subgroups**

Safety in the following subgroups will be analyzed.

1. Children (<15 years), adults ( $\geq 15$  years).
2. Elderly ( $\geq 65$  years), non-elderly (<65 years).
3. Presence or absence of pregnancy.
4. Presence or absence of hepatic dysfunction.
5. Presence or absence of renal dysfunction.
6. By indication.
7. By whether criteria for proper use are met.
8. History of hepatitis B, tuberculosis, and herpes zoster.
9. Severity of hepatic dysfunction.
10. Sex.

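### Risk factors for interstitial lung disease are compared by crude incidence although observation follows time on drug, so a factor that shortens treatment for other reasons can look protective

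*SAP*

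**What the plan says.** Protocol section 1 makes the onset and possible risk factors of interstitial lung disease (ILD) the third objective. SAP 6.1 repeats this as a safety endpoint: "Potential risk factors of interstitial lung disease".

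The visible by-factor analysis is in SAP 8.2.6, under incidence of adverse reactions by patient demographic. It gives the number and percentage of patients with an adverse reaction for each item in SAP 10.1.1, and says that Fisher's "exact test will be performed for nominal scale data and Cochran-Armitage test (exact method) for ordered scale data". For ILD and five other major items it says: "Tabulation will be performed in the same manner for interstitial lung disease". Whether the tests carry over to ILD is not stated.

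Observation time depends on treatment time. Protocol 5.4 ends adverse-event follow-up at Week 24, with the exception: "If the drug is discontinued before Week 24, observe until Day 28 after the discontinuation of administration". Patients who enter the long-term surveillance are "observed for up to 96 weeks after the start of administration". SAP 8.2 says that, unless otherwise specified, "data from the all patient surveillance and data from the long-term use surveillance will be tabulated and analyzed together".

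The plan expects wide variation. Protocol section 3 assumes the "discontinuance/drop-out rate at 12 weeks in this study will be increased by 10% to 50" per cent, and SAP 2.1.2 says "it is assumed that 20% of the cases included in the all patient surveillance will be registered in this study", about 120 of 600.

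**The concern.** The denominator is patients, but the chance of being recorded with ILD also depends on weeks observed. A patient who stops after one dose is observed for about 4 weeks; a long-term patient may be observed for 96. Protocol section 3 reports that ILD was seen from Week 4 onward, so the earliest stoppers have little or no time in which it could be recorded.

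Several listed factors could plausibly affect how long treatment lasts, for example performance status, MSKCC risk group and whether the proper-use criteria are met. The reasons for stopping in Protocol 6.7 include insufficient effectiveness, other adverse events and death. If a factor shortens treatment by such routes, its crude ILD percentage falls whatever its effect on ILD. A neutral factor can look protective, and a harmful one is pulled toward the null or past it. Because the results feed proper-use information, a missed risk factor is the error that matters, and the crude table gives no sign of it.

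The argument does not apply in this form to a factor that shortens treatment by causing ILD, because those cases are counted.

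**Working it through.** **The plan's own figures reproduce.** With 300 patients, the probability of at least one event at 1.0% is 0.951, and of at least 40 ILD cases at 17.1% is 0.968. 300/(1 − 0.50) = 600, and 600 × 0.20 = 120. The sample-size rationale is not in question.

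**Inputs from the documents.** Overall ILD 17.1%; onset from Week 4; mean 12-week retention 50%; observation to 4 weeks after stopping, capped at Week 24, or at Week 96 if re-registered; 20% re-registered.

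**Inputs assumed, because the documents do not give them.** Retention by factor level, the shape of the ILD hazard, the group split, and exponential time on drug that is independent of ILD.

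**Formula.** With 12-week retention r, the stopping rate is d = −ln(r)/12 per week. For a constant ILD hazard h from Week 4 and cap C,

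P(ILD) = h/(h + d) × [1 − exp(−(h + d)(C − 4))].

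h is set so that the two groups average 17.1%.

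**Worked case: 24-week window, retention 40% vs 60%, no true effect.** d = 0.0764 and 0.0426; h = 0.0164.

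- 40% group: 0.0164/0.0928 × (1 − e^(−1.855)) = 14.9%
- 60% group: 0.0164/0.0590 × (1 − e^(−1.179)) = 19.3%
- Ratio: 0.77

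If ILD arises only in Weeks 4 to 12, C is replaced by 12. For the pooled data, patients on drug beyond Week 24 are followed to Week 96 with probability p. At 40% vs 60%, (0.40² + 0.60²)/2 = 26% are still on drug at Week 24, so p = 0.20/0.26 = 0.77 gives the planned 120. The alternative is p = 20/35, from the planned 20% registered against the 35% treated for 24 weeks or longer in the trials. The two values of p give the ranges in the last column.

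| 12-week retention | True hazard ratio | Weeks 4–12 only | 24-week window | Pooled to Week 96 |
|---|---|---|---|---|
| 40% vs 60% | 1 | 0.89 | 0.77 | 0.65–0.68 |
| 45% vs 55% | 1 | 0.94 | 0.88 | 0.80–0.82 |
| 48% vs 52% | 1 | 0.98 | 0.95 | 0.92–0.93 |
| 40% vs 60% | 1.5 | 1.28 | 1.10 | 0.91–0.95 |

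With equal retention, a hazard ratio of 1.5 gives a crude ratio of 1.40 to 1.44.

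**If ILD is tested.** The table shows how often Fisher's test rejects at two-sided 5% with no true effect (4,000 simulations per cell).

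| Retention | Split | Weeks 4–12 only | 24-week window | Pooled |
|---|---|---|---|---|
| 40% vs 60% | 300/300 | 9% | 25% | 53–63% |
| 40% vs 60% | 150/450 | 8% | 18% | 39–41% |
| 40% vs 60% | 60/540 | 5% | 9% | 16–19% |
| 45% vs 55% | 300/300 | 5% | 9% | 16–20% |
| 45% vs 55% | 60/540 | 4% | 5% | 7% |

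A log-rank test censored at the end of observation rejects in 4% to 6% of the same runs. With a true hazard ratio of 1.5, 40% vs 60% and 300/300, Fisher rejects in 24%, 7% and 4–6% across the three settings; log-rank rejects in 51% to 54%.

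**Counter-case.** If the factor acts only through ILD (hazard ratio 2, ILD ends treatment, 24-week window), 12-week retention is 47% vs 51%, crude ILD is 22% vs 12%, and Fisher rejects in 90% of runs, never in the protective direction.

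**The case against.** **The analysis may exist but be redacted.** A block at the end of SAP 8.2.6 is blacked out, and the change log shows that further analyses, including duration of treatment, were placed in that section. The ILD risk-factor endpoint has no visible heading of its own. This stands: the point concerns the visible SAP, and the fix is conditional.

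**Time is partly handled.** SAP 8.1.4 gives Kaplan-Meier quartiles and plots, and 8.2.5 tabulates duration of observation. SAP 8.2.6 has ILD cumulative-incidence graphs and tabulates ILD onset time by lung-disease history and baseline imaging. SAP 10.1.1 excludes the treatment-duration and cumulative-dose items from testing. None of these compares factors per time at risk.

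**ILD may not be tested at all.** The test sentence covers all adverse reactions, and tests are not confirmatory under SAP section 4. This stands as a reason to treat the rejection rates as secondary. The crude ratios need no test.

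**The size rests on assumptions.** This also stands. The largest figures need a 20-point retention gap, and the highest rejection rates also need an even split and a constant hazard to Week 96.

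**Crude incidence is a legitimate quantity.** It describes risk over treatment as received. The difficulty arises when it is read as a screen for risk factors.

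**Log-rank does well partly by construction.** Stopping was simulated as independent of ILD. In practice early lung symptoms can prompt interruption or stopping, and imaging-only cases depend on when a CT is taken. An unadjusted log-rank over a long factor list also adds tests and leaves confounding untouched. These are real limits and should be stated with the results.

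**Conclusion.** The concern holds for the visible SAP. Comparing ILD across factors by crude incidence mixes the ILD hazard with time under observation, and the bias favours any factor that shortens treatment for reasons other than ILD.

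How much this matters depends on three things the documents do not give: the retention gap between factor levels, how late ILD arises, and how common the factor is. It is close to negligible for a 48% vs 52% gap with hazard confined to Weeks 4 to 12. It is large enough to hide or reverse a true hazard ratio of 1.5 at 40% vs 60% once the long-term data are pooled. As the surveillance is not confirmatory and the crude tables remain valid as description, this is an inexpensive improvement to consider and does not undermine the design.

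**What to change.** Unless the redacted part of SAP 8.2.6 already does so:

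- Add a supportive comparison of time to first ILD for each SAP 10.1.1 item that is open to testing: log-rank (trend version for ordered items) or a cause-specific Cox hazard ratio with 95% confidence interval.
- Define censoring as the end of adverse-event observation: 28 days after stopping, Week 24 if not re-registered, otherwise the end of long-term follow-up. Protocol 6.8 ends the reportable period at the start of a new treatment; clarify whether this covers all adverse events or only a fatal tumour event, and censor there only in the first case.
- Keep the crude tables, labelled as risk over treatment as received, and state whether the Fisher and Cochran-Armitage tests apply to ILD.
- Show the number still under observation for ILD onset intervals after Week 24.
- State as a limitation that the method assumes stopping is not itself driven by early lung symptoms.

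The cost is SAP wording and modest programming. Administration dates (Protocol 6.2) and onset dates (Protocol 6.8) are already collected, so no new data are needed. The downsides are some extra output and reliance on non-informative stopping.

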6.8 Adverse event

To evaluate safety, the onset of adverse events after the start of the drug administration will be investigated and the following information (1) to (9) will be recorded. In principle, each adverse event will be followed until each safety evaluation date. If an adverse event occurs, the investigator will give appropriate treatment, readily notify the sponsor as specified in the "Adverse Event Reporting" (attachment), and, in principle, follow its outcome and clinical course until its symptom is resolved. Particularly, the investigator will call by phone the following contact number within 24 hours "when a serious adverse event occurs", "when a patient or his/her partner becomes pregnant or is found to be pregnant during the treatment with this drug regardless of the onset of adverse events", or when the investigator knows any additional information on the adverse event or pregnancy. For details, refer to the "Adverse Event Reporting" (attachment).

Contact number in case of serious adverse event

| | |
|------------------|---|
| [TEL] | [name] (toll-free) |
| [Business hours] | 9:00 to 18:00 (available every day of the year) |

In addition, a detailed study will be separately conducted for intrauterine exposure, serious adverse reactions, or adverse reactions not listed in the package insert, etc., if deemed necessary by the sponsor.

- [1] Date of safety evaluation
- [2] Presence/absence of adverse events
- [3] Adverse event name (disease or symptom name)
- [4] Date of onset
- [5] CTCAE v4.0 Grade
- [6] Treatment
- [7] Seriousness
- [8] Current outcome of adverse event
- [9] Causal relationship

Important: Adverse events are any and all unfavorable events (including clinically significant abnormal changes in laboratory tests) occurring in patients after starting the target drug treatment regardless of their causal relationship. Serious adverse events are any unfavorable medical occurrences that result in death, are life-threatening, require (or prolong) hospitalization, cause persistent or significant disability/incapacity, result in congenital anomalies or birth defects, or are other conditions which represent significant health hazards.

Supplementary information:

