## 7. HANDLING OF MISSING DATA

Not applicable.

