#### **8.1.4. Analysis of Time Data (time to the onset of event)**

Ninety-five percent confidence intervals for median, first quartile, and third quartile by the Kaplan-Meier method will be calculated. In addition, Kaplan-Meier plots will be prepared.

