11. Complications.

The number of patients with adverse reactions, serious adverse reactions, and CTCAE Grade  $\geq 3$  adverse reactions and the incidence of these adverse reactions will be calculated by SOC and PT.

For items using reference values, results using corporate reference values will be tabulated in addition to results using institutional reference values.

- **Major investigation items**

The number of patients with adverse reactions falling under major investigation items and the incidence of these adverse reactions will be calculated by SOC and PT. The number of patients with adverse events and the incidence of adverse events will be tabulated in the same manner.

The same tabulation will be performed for each of the following items.

1. Interstitial lung disease.
2. A wide range of related events suspected of interstitial lung disease.
3. Dyspnea.
4. Diabetes mellitus/hyperglycemia.
5. Hypersensitivity reaction.
6. Diarrhea.
7. Hypophosphatemia.
8. Hypokalemia.
9. hypercholesterolemia/hyperlipidemia.
10. Infection.
11. Intracerebral hemorrhage.
12. Abnormality in wound healing.
13. Mucositis-related adverse events.
14. Skin disorder.
15. Acute renal failure.
16. Gastrointestinal perforation.

- **Further tabulation of interstitial lung disease**

The number of patients with adverse reactions and adverse events of interstitial lung disease and the incidences of these adverse reactions and adverse events will be tabulated by presence or absence of past or present history of lung disease and presence or absence of abnormal imaging findings at the initiation of treatment by category shown below.

- Seriousness;
- Clinical symptoms;
- Severity (CTCAE Grade);
- Time from the initiation of treatment to initial onset (weeks);
- Cumulative duration (weeks);
- Imaging findings suspected of interstitial lung disease.

The worst CTCAE Grade and treatment effect will be tabulated by presence or absence of treatment of interstitial lung disease.

The outcome in patients in whom interstitial lung disease was CTCAE Grade 1 at onset will be tabulated by status (continued/discontinued) of treatment.

The list of the course of interstitial lung disease and the list of the time course of CTCAE Grade will be prepared.

Graphs of time from the initiation of treatment to initial onset (weeks), outcome, and administration of this drug will be prepared by CTCAE Grade at onset. Graphs will be prepared in the same manner by maximum CTCAE Grade.

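### Interstitial lung disease (ILD) duration is tabulated without separating resolved, ongoing and fatal cases and without a censoring or death rule, so unresolved or rapidly fatal ILD can fall in the short-duration categories.

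*SAP*

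**What the plan says.** ILD duration is a named safety item. SAP 6.1 item 7, matching Protocol 7.2.1 item 7, reads "Characteristics of interstitial lung disease (imaging findings, onset timing, duration, and breakdown by severity".

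The SAP delivers it in section 8.2.6, under the further tabulation of ILD. Patients with ILD are counted by several categories, one of which is "Cumulative duration (weeks". The counts are split by "presence or absence of past or present history of lung disease and presence or absence of abnormal imaging findings at the initiation of treatment". Outcome is neither a stratifier nor a category in that table. No start rule, stop rule, cut points or treatment of repeat episodes is given.

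Four other places bear on it:
- SAP 7, "HANDLING OF MISSING DATA", says only that the topic does not apply.
- The Kaplan-Meier method in SAP 8.1.4 stands under "Analysis of Time Data (time to the onset of event", so its stated scope is onset, not resolution.
- SAP 6.1 item 10 has a rule for treatment duration: "Patients for whom the completion of treatment is not reported in this study will be censored at the date of last dose". SAP 6.2 has event and censoring rules for progression-free survival. Neither covers ILD duration.
- For early discontinuation, Protocol 5.4 says to "observe until Day 28 after the discontinuation of administration". The supplementary text in Protocol 6.8 closes the reportable period when a new treatment starts. Protocol 6.8 also states "In principle, each adverse event will be followed until each safety evaluation date", and later in the same paragraph asks for follow-up, in principle, until the symptom resolves.

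**The concern.** A duration can be read directly only for a case whose end was seen. For an ongoing case, the recorded time is a lower bound. For a fatal case, the time to death is not a time to recovery. A table that mixes the three puts a patient who died within a week in the same cell as one who recovered within a week. It also puts a case last seen at four weeks with a case that cleared at four weeks.

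Truncation is probably not random. The label criteria reproduced in Protocol section 2 link discontinuation to the more severe ILD categories, and discontinuation starts the 28-day limit. Some of the worst cases may therefore have the shortest observed times.

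ILD is the subject of the study's third objective, and the results feed proper-use information. An error towards shorter duration would be in the reassuring direction.

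**Working it through.** **The plan's own figure.** The documents give no figure for ILD duration. The nearest is the number of cases that would fill the table: at least 40 with probability at least 95% (Protocol 3). With X ~ Binomial(300, 0.171), P(X ≥ 40) = 0.968, so the statement reproduces. The expected count is 300 × 0.171 = 51.3, or 600 × 0.171 = 102.6 if all 600 patients are used.

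**Inputs for the effect on duration.** All are assumptions. Time to resolution is exponential with median m weeks. A fraction f of cases is fatal, with exponential time to death, median 2 weeks. The central values are m = 8 and f = 0.10. Four weeks is used as a convenient cut because the 28-day limit equals it; the SAP sets no cut points.

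**Formulas.**
- Truly resolved by 4 weeks: R = (1 − f)(1 − 2^(−4/m)).
- Ended by 4 weeks, by resolution or death: E = R + f(1 − 2^(−4/2)) = R + 0.75f.
- Tabulated at 4 weeks or less, if observed time is entered and follow-up lasts C weeks from onset: 1 − P(C > 4)(1 − E).
- Median time to resolution with deaths counted as never resolved: m × log2[(1 − f)/(0.5 − f)].

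**Central case.** R = 0.9 × 0.2929 = 0.264. E = 0.264 + 0.075 = 0.339. The median time to resolution is 8 × log2(0.9/0.4) = 9.4 weeks.

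| Follow-up assumed | Tabulated at ≤4 weeks | Resolved by 4 weeks |
|---|---|---|
| Every case to resolution or death | 34% | 26% |
| Onset uniform over Weeks 4–24, observation ends at Week 24 | 1 − 0.8 × 0.661 = 47% | 26% |
| Same onset, four further weeks of observation | 34% | 26% |
| All stop at onset, seen for 28 days | 100% by construction | 26% |

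In the second row, C is uniform on 0–20 weeks, so P(C > 4) = 0.8, and 44% of cases are ongoing at the cut-off. The median observed time solves (1 − t/20)[0.9 × 2^(−t/8) + 0.1 × 2^(−t/2)] = 0.5, giving t = 4.4 weeks against 9.4. In the last row, 66% are ongoing.

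**Range.** With the Week 24 cut-off, m from 4 to 12 and f from 0 to 0.20, the median observed time is 2.7 to 5.9 weeks, and the median time to resolution is 4.0 to 17.0 weeks. The observed median is the shorter one in every combination.

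**Complete follow-up.** The gap then comes from deaths alone. At f = 0.15, R = 0.85 × 0.2929 = 0.249 and E = 0.249 + 0.1125 = 0.361, so 36% against 25%. At f = 0 there is no gap.

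**Resolved cases only.** With a 28-day limit and m = 8, the median among cases seen to resolve solves 1 − 2^(−t/8) = 0.5 × 0.2929. This gives t = 1.8 weeks, against 8 weeks among all who eventually recover. Leaving out the ongoing cases therefore shortens the result too.

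**The case against.** The strongest reply is that the SAP leaves duration undefined and does not misdefine it. It nowhere says that observed weeks are entered, and a count by category leaves room for an ongoing or unknown row. That stands. An unknown row, however, leaves the numbered rows as a resolved-only table unless deaths are also removed, and a resolved-only table is short as well.

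Second, fatal and unresolved ILD is visible elsewhere. SAP 8.2.6 tabulates ILD by CTCAE Grade and the worst Grade by treatment of ILD. It graphs outcome by onset and maximum Grade, and it lists the course and the Grade over time. Deaths are listed in SAP 9. This also stands, and with about 40 cases a patient reader could pair duration with outcome from the course list. It does not correct the summary table. In addition, the outcome categories given in SAP 8.2.6 for adverse reactions contain no fatal category, although Grade 5 is listed.

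Third, truncation may be modest. Protocol 6.8 asks for follow-up to resolution, and long-term data to Week 96 are pooled. The label criteria do not lead to discontinuation in every ILD category. This stands and limits the size.

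Two stronger readings are tempting. A reader might infer that the plan will report unresolved and fatal ILD as short-lasting. The documents do not support this, because no such rule is written. A reader might also infer that most cases will show four weeks or less. That result follows almost entirely from assuming that most patients stop at onset and are then seen for only four weeks. If 70% do so, at least 70% must show four weeks or less. It also sets aside the follow-up-to-resolution statement.

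Finally, text at the end of SAP 8.2.6 is blacked out and the detailed ILD form is not shown, so further handling of duration there cannot be excluded.

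**Conclusion.** The point holds in limited form. A named ILD endpoint is summarised in a table that, on the visible text, does not distinguish resolved, ongoing and fatal cases and has no censoring or death rule. Unresolved or rapidly fatal ILD can fall in the short-duration categories, and a resolved-only version would also be biased short.

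The direction is consistent under both natural ways of filling the table. The size is not determined by the documents: it depends on how far follow-up to resolution was achieved and on the fatality of ILD, neither of which is given. Under the assumed central case, the excess at 4 weeks or less is 8 percentage points with complete follow-up (34% against 26%) and 21 points with a Week 24 cut-off (47% against 26%). With complete follow-up and no deaths it is zero.

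This should be corrected before the duration table is used for proper-use information. It does not show that fatal or unresolved ILD is hidden in the report as a whole.

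**What to change.** In SAP 8.2.6:
- Define cumulative duration: start date, stop date, and how repeat episodes are added.
- Tabulate it separately for cases resolved, ongoing at last report, and died.
- Add the cumulative incidence of resolution from onset (Aalen-Johansen estimate), with ongoing cases censored at last report and death as a competing event. Give 95% confidence intervals and the number still at risk at each reported time. State which episode is analysed when ILD recurs.
- State that censoring may be informative, because stopping treatment is linked to severity.

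Reconcile the two follow-up statements in Protocol 6.8, and say in the SAP which one the collected data reflect. Deleting one is not needed and would not recover data: the surveillance was planned to run to March 2014, and this SAP version is dated September 2016.

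The same duration item appears for the five other events with further tabulations in SAP 8.2.6, so the definition can be shared.

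The cost is a few lines of SAP text and one additional table. Precision will be limited. With 40 cases and none censored, the half-width for a proportion near 50% is 1.96 × √(0.25/40) = 0.155, about 15 percentage points, and it widens at later times. The table also needs resolution dates. The adverse event items in Protocol 6.8 list an onset date and a current outcome but no resolution date, so confirm first that the detailed ILD form holds it.
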